4.6.3. Laboratory Safety Variables

The following laboratory tests will be collected and summarized:

Blood Chemistry

Sodium	Total protein, serum
Potassium	Creatinine
Chloride	Blood urea nitrogen (BUN)
Carbon dioxide	Aspartate aminotransferase (AST)
Calcium	Alanine aminotransferase (ALT)
Glucose	Total bilirubin
Albumin	

Hematology

Hemoglobin	Differential:
Hematocrit	Neutrophils
Red blood cells (RBCs)	Lymphocytes
White blood cells (WBCs)	Monocytes
Red cell indices	Basophils
Platelet count	Eosinophils

4.6.4. Vital Signs

The following vital signs parameters will be recorded and summarized:

- Body temperature
- Blood pressure
- Pulse rate
- Respiration rate

4.6.5. 12-Lead Electrocardiography (ECG)

12-Lead ECG parameters are not collected in this study.

4.6.6. Physical Examination Variables

Physical examination will be conducted at the protocol scheduled visits. If any abnormal findings during the screening period, they will be recorded in medical history eCRF form and AE eCRF form for any new or worsening abnormal findings during post-screening period.

4.6.7. Other Safety Variables

Not applicable.

4.7. Pharmacokinetic Variables

The PK variables are concentrations of casirivimab and imdevimab in serum and sampling time. The sampling time points are specified in [Table 3](#) in the protocol.

The analysis of PK will be documented in a separate document.

4.8. Immunogenicity Variables

The immunogenicity variables include ADA status and titer at nominal sampling time/visit. Serum samples for ADA will be collected at the clinic visits specified in the protocol SOE. Samples positive in the ADA assay will be further characterized for ADA titers.

5. STATISTICAL METHODS

Unless otherwise stated, the following conventions will be applied when presenting summary level statistics for data.

Continuous variables will be summarized within each body weight group by presenting the following summary statistics: number of participants with an available value of the variable (n), mean, standard deviation, median, minimum, maximum, 1st quartile and 3rd quartile.

Categorical data will be summarized within each body weight group by presenting the frequency (i.e. total number of participants within each level of the categorical variable in a given body weight group). All levels of the categorical variable will be included. Percentages will also be calculated for each level of the categorical variables with respect to the total sample size of the respective treatment arm.

In general, summaries will display grouping by weight group, and by all participants combined. Weight groups are defined according to protocol section 8.1. Weight group A: ≥ 10 kg to < 40 kg, and weight group B: ≥ 3 kg to < 10 kg. Within each weight group, sub groups are further defined in the SAP according to weight based dosing categories: weight group A1: ≥ 20 kg to < 40 kg, weight group A2: ≥ 10 kg to < 20 kg; weight group B1: ≥ 5 kg to < 10 kg, and weight group B2: ≥ 3 kg to < 5 kg.

5.1. Demographics and Baseline Characteristics

Demographic and baseline characteristics will be summarized via descriptive statistics based on SAF population. A participant listing will be provided.

5.2. Medical History

Medical history will be summarized by SOC then PT. A participant listing will be provided.

5.3. Prior/concomitant Illnesses and Medications

Medications and procedures will be summarized based on SAF using descriptive statistics.

Prior/concomitant medications will be summarized by ATC level 2 and ATC level 4.

Prior/concomitant procedures will be summarized by SOC and PT.

Listings will also be provided.

Participants who received COVID 19 vaccine and their time to first COVID 19 vaccine (days) from the study treatment administration including the following categories: ≤ 90 days and > 90 days, will be summarized using descriptive statistics.

5.4. Prohibited Medications

Prohibited medications is defined as any non-permitted medication as outlined within Section 8.7.1 of the protocol. They will be reviewed and identified by the study clinician and reported in protocol deviations.

5.5. Participant Disposition

Enrolled participants are defined as those who signed an informed consent form. Screen-failed participants are collected from participants screening status and eligibility eCRF form and summarized. Listing of participant disposition will be provided.

Participant counts of those screened, enrolled, the completion status for the study (along with reason for any study withdrawal) will be summarized.

5.6. Extent of Study Treatment Exposure and Compliance

Exposure data will be summarized based on SAF using descriptive statistics. Listings will also be provided. Participants with a complete or delayed dose administration (completed SC dose administered) will be summarized.

5.6.1. Measurement of Compliance

Treatment compliance is not applicable as this is a single-dose study.

5.6.2. Study Observation Duration

Study observation duration (days) will be summarized and is defined as:

Study observation duration = (date of the last study visit - date of study treatment administration) + 1

5.7. Analyses of Efficacy Variables

5.7.1. Analysis of Primary Efficacy Variable(s)

Not applicable

5.7.2. Analysis of Secondary Efficacy Variables

Not applicable.

5.8. Analysis of Safety Data

For safety variables, two observation periods are defined:

- Pre-treatment period is defined as the time from signing the Informed Consent Form (ICF) to the time before administration of study drug
- On-treatment period is defined as the time after administration of study drug until the end of study.

Safety data will be summarized for all participants based on SAF using descriptive statistics unless noted otherwise.

5.8.1. Adverse Events

All AEs reported in this study will be coded using the Medical Dictionary for Regulatory Activities (MedDRA). The verbatim text, the PT, and the primary SOC will be listed in participant listings.

Treatment-emergent adverse events (TEAEs) are defined as those that are not present at baseline or represent the exacerbation of a pre-existing condition during the on-treatment period.

The focus of adverse event reporting in the clinical study report will be on TEAEs. A listing will be provided for COVID-19 Signs and Symptoms.

For details on handling missing data and partial dates, see Section [6](#).

Summaries of all TEAEs will include:

- Overview of TEAEs
- The number (n) and percentage (%) of participants with at least 1 TEAE by SOC and PT
- TEAEs by severity (according to the grading scale outlines in protocol section 10.2.4), presented by SOC and PT
- Treatment-related TEAEs presented by SOC and PT
- Treatment-emergent AESIs by SOC and PT
- Treatment-emergent hypersensitivity events by SMQ hypersensitivity (narrow) and PT

5.8.2. Analysis of Adverse Events of Special Interest

Hypersensitivity events will be presented by SMQ hypersensitivity (narrow) and PT, as well as SOC and PT according to eCRF, respectively. Other treatment-emergent AESIs will be presented by SOC and PT. The summaries will be sorted by decreasing incidence of PT within each SOC/SMQ based on all participants combined column.

5.8.3. Clinical Laboratory Measurements

Individual participant laboratory parameter measurements will be evaluated by PCSV criteria (See [Appendix 10.1](#)), specifically identifying participants with at least one post-baseline measurement that meets the PCSV criteria. These laboratory parameters will be presented by the biological functions (e.g. red blood cells and platelets, white blood cells, and liver function, etc.). The incidence of PCSVs at any time including data from unscheduled visits during the study period will be summarized.

Listings of laboratory measurements at all timepoints for the participants that meet PCSV criteria will be provided. Listings of all local laboratory measurements will also be provided.

A listing of all women of childbearing potential with a confirmed serum pregnancy test during the study will be provided.

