7.2. Study Population

7.2.1. Inclusion Criteria

Subjects must meet the following criteria to be eligible for inclusion in the study:

1. Is <12 years of age and ≥ 3 kg to <40 kg at the time parental/guardian consent is signed
2. Has at least one risk factor for developing severe COVID-19 if they were to become infected, such as:
 - a. Obesity (BMI [kg/m^2]) $\geq 95^{\text{th}}$ percentile for age and sex based on CDC growth charts)
 - b. Cardiovascular disease
 - c. Chronic lung disease
 - d. Type 1 or type 2 diabetes mellitus
 - e. Chronic kidney disease, including those on dialysis
 - f. Chronic liver disease
 - g. Immunocompromised or immunodeficient, based on Investigator's assessment (examples include cancer treatment, bone marrow or organ transplantation, immune deficiencies, HIV infection, sickle cell anemia, thalassemia, and prolonged use of immune-weakening medications)

- h. Medical complexities (examples include any underlying genetic condition, neurologic condition, metabolic condition, or congenital heart disease)
- i. **Any other condition** deemed by the Investigator to be a risk factor for severe COVID-19

- 3. Is willing and able to comply with clinic visits and study-related procedures
- 4. Has provided informed consent signed by subject or legally acceptable representative

Note: Age-appropriate assent will be collected from the study subject according to local regulatory (competent authority/ethics) guidelines.

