11.4.3.2. Other Safety

Vital Signs

Vital signs (temperature, pulse, blood pressure, and respiration rate) will be summarized by baseline and change from baseline to each scheduled assessment time with descriptive statistics.

Laboratory Tests

Laboratory test results will be summarized by baseline and change from baseline to each scheduled assessment time with descriptive statistics.

Number and percentage of subjects with a potentially clinically significant value (PCSV) at any post-study drug administration time point will be summarized for each clinical laboratory test for all subjects and separately for subjects in whom the PCSV criterion was normal or missing at baseline.

Shift tables based on baseline normal/abnormal and other tabular and graphical methods may be used to present the results for laboratory tests of interest.

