1.2.3. Modifications from the Statistical Section in the Final Protocol

The NAb analysis specified in section 11.4.5.2 in protocol will not be performed.

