2.2. Sample Size and Power Considerations

There are no formal hypotheses in this study. The sample size was chosen based on PK considerations and is consistent with early phase studies to assess PK.

At least 12 participants are needed to enroll in each weight group (Group A: ≥ 10 kg to < 40 kg, and Group B: ≥ 3 kg to < 10 kg) to assess drug concentration. The study plans to enroll approximately 28 participants in total.

The sample size may be adjusted if planned SC dosing of casirivimab+imdevimab does not achieve concentrations in serum similar to, or higher than, that observed in adults (≥ 18 years of age) after casirivimab+imdevimab 1200 mg (600 mg per mAb) SC administration. PK will be evaluated on an ongoing basis to determine if dose adjustments are needed and whether more participants are needed for analysis.

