WBC	<3.0 Giga/L or <LLN (if LLN ≤3.0 Giga/L) and baseline ≥3.0 Giga/L or ≥LLN (if LLN≤3.0 Giga/L) (Non-Black); <2.0 Giga/L or <LLN (if LLN ≤2.0 Giga/L) and baseline ≥2.0 Giga/L or ≥LLN (if LLN≤2.0 Giga/L) (Black) ≥16.0 Giga/L or ≥ULN (if ULN ≥16.0 Giga/L) and baseline < 16 Giga/L or <ULN (if ULN ≥16.0 Giga/L)	
Lymphocytes	>4.0 Giga/L or >ULN (if ULN ≥4.0 Giga/L) and baseline ≤4.0 Giga/L or ≤ULN (if ULN ≥4.0 Giga/L)	
Neutrophils	<1.5 Giga/L or <LLN (if LLN ≤1.5 Giga/L) and baseline ≥1.5 Giga/L or ≥LLN (if LLN ≤1.5 Giga/L) (Non-Black); <1.0 Giga/L or <LLN (if LLN ≤1.0 Giga/L) and baseline ≥1.0 Giga/L or ≥LLN (if LLN ≤1.0 Giga/L) (Black)	
Monocytes	>0.7 Giga/L or >ULN (if ULN ≥0.7 Giga/L) and baseline ≤0.7 Giga/L or ≤ULN (if ULN ≥0.7 Giga/L)	
Basophils	>0.1 Giga/L or >ULN (if ULN ≥0.1 Giga/L) and baseline ≤0.1 Giga/L or ≤ULN (if ULN ≥0.1 Giga/L)	
Eosinophils	>0.5 Giga/L or >ULN (if ULN ≥0.5 Giga/L) and baseline ≤0.5 Giga/L or ≤ULN (if ULN ≥0.5 Giga/L)	

Parameter	PCSV	Comments
Hemoglobin	
≤ 115 g/L or \leqLLN (if LLN ≤ 115 g/L) and baseline > 115 g/L or $>$LLN (if LLN ≤ 115 g/L) for male; ≤ 95 g/L or \leqLLN (if LLN ≤ 95 g/L) and baseline > 95 g/L or $>$LLN (if LLN ≤ 95 g/L) for Female.
 
≥ 185 g/L or \geqULN (if ULN ≥ 185 g/L) and baseline < 185 g/L or $<$ULN (if ULN ≥ 185 g/L) for Male; ≥ 165 g/L or \geqULN (if ULN ≥ 165 g/L) and baseline < 165 g/L or $<$ULN (if ULN ≥ 165 g/L) for Female
 
Decrease from Baseline ≥ 20 g/L
	Three criteria are independent.
Hematocrit	
≤ 0.37 v/v or \leqLLN (if LLN ≤ 0.37 v/v) and baseline > 0.37 v/v or $>$LLN (if LLN ≤ 0.37 v/v) for Male; ≤ 0.32 v/v or \leqLLN (if LLN ≤ 0.32 v/v) and baseline > 0.32 v/v or $>$LLN (if LLN ≤ 0.32 v/v) for Female
 
≥ 0.55 v/v or \geqULN (if ULN ≥ 0.55 v/v) and baseline < 0.55 v/v or $<$ULN (if ULN ≥ 0.55 v/v) for Male; ≥ 0.5 v/v or \geqULN (if ULN ≥ 0.5 v/v) and baseline < 0.5 v/v or $<$ULN (if ULN ≥ 0.5 v/v) for Female
	Two Criteria are independent
RBC	≥ 6 Tera/L or \geq ULN (if ULN ≥ 6 Tera/L) and baseline < 6 Tera/L or $<$ ULN (if ULN ≥ 6 Tera/L)	
Platelets	
< 100 Giga/L or $<$LLN (if LLN ≤ 100 Giga/L) and baseline ≥ 100 Giga/L or \geqLLN (if LLN ≤ 100 Giga/L)
 
≥ 700 Giga/L or \geqULN (if ULN ≥ 700 Giga/L) and baseline < 700 Giga/L or $<$ULN (if ULN ≥ 700 Giga/L)
	Two independent criteria

Parameter	PCSV	Comments
Vital signs		
HR	<45 bpm and decrease from baseline \geq 20 bpm \geq 120 bpm and increase from baseline \geq 20 bpm	

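### The SAP drops the protocol's all-subjects count of laboratory PCSVs without declaring it, so on 15 of 20 tests a child who starts beyond the PCSV threshold cannot be counted

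*SAP*

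**What the plan says.** Protocol 11.4.3.2 (Other Safety) asks, for each laboratory test, for the number and percentage of subjects with a PCSV at any time after dosing, "for all subjects and separately for subjects in whom the PCSV criterion was normal or missing at baseline".

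SAP 5.8.3 applies the Appendix 10.1 criteria, "specifically identifying participants with at least one post-baseline measurement that meets the PCSV criteria". It then plans one summary: "The incidence of PCSVs at any time including data from unscheduled visits during the study period will be summarized". It does not split that summary by baseline status.

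Most Appendix 10.1 criteria contain a baseline condition. The low-neutrophil row, for instance, continues "and baseline ≥1.5 Giga/L or ≥LLN (if LLN ≤1.5 Giga/L) (Non-Black". If the baseline is missing, the appendix judges the post-baseline value alone.

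SAP 1.2.3 lists one departure from the protocol's statistical section: "The NAb analysis specified in section 11.4.5.2 in protocol will not be performed".

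**The concern.** With the baseline condition built in, the SAP's single count is in effect the protocol's second count. The first has disappeared, and someone reading both documents would not learn this from the list of modifications.

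The population makes it relevant. Protocol 7.2.1 admits children with chronic kidney or liver disease, children on cancer treatment or after transplant, and those with "immune deficiencies, HIV infection, sickle cell anemia, thalassemia, and prolonged use of immune-weakening medications". Baseline values past some of these cut-offs are foreseeable. Such a child can move much further out without entering the PCSV numerator. SAP section 5 takes percentages of the whole group by default, so the same child would still sit in the denominator. The table would then read as an incidence in everyone when some participants could not contribute to it.

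**Working it through.** There is no sample-size or power figure to reproduce. The SAP states "There are no formal hypotheses in this study", and the point is about a counting rule.

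**1. Tests with a criterion.** Protocol 9.2.5 and SAP 4.6.3 list 13 chemistry and 11 hematology items: 13 + 11 = 24. Carbon dioxide, calcium, total protein and red cell indices have no row in Appendix 10.1: 24 − 4 = 20. The tally leaves out analytes not collected, derived creatinine clearance and the combined ALT and bilirubin criterion.

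**2. Tests with a route for a child already at PCSV level.**
- ALT, AST and total bilirubin have higher tiers.
- Creatinine has changes of at least 30% and at least 100%, with no baseline condition.
- Hemoglobin has a fall of at least 20 g/L, with no baseline condition.

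That is 5 tests. The other 20 − 5 = 15 (15/20 = 75%) have no route in the same direction: sodium, potassium, chloride, glucose, albumin, BUN, hematocrit, RBC, WBC, platelets, neutrophils, lymphocytes, monocytes, basophils and eosinophils.

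**3. Worked pairs.** The documents give no local lower limits of normal (LLN), so those shown are assumptions.

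| Test | Baseline to later value | SAP criterion | Threshold alone |
|---|---|---|---|
| Platelets, Giga/L (LLN 150) | 200 to 40 | counted | counted |
| Platelets (LLN 150) | 120 to 90 | counted | counted |
| Platelets (LLN 150) | 90 to 20 | not counted | counted |
| Platelets (LLN above 95) | 95 to 15 | not counted | counted |
| Neutrophils, Giga/L, non-Black (LLN above 1.4) | 1.4 to 0.2 | not counted | counted |
| ALT, × ULN | 4 to 8 | counted (tier above 5) | counted |
| ALT, × ULN | 6 to 9.5 | not counted | counted |
| ALT, × ULN | 21 to 60 | not counted | counted |
| Hemoglobin, g/L, boy (LLN above 105) | 105 to 84 (fall 21) | counted (fall rule) | counted |
| Hemoglobin, boy (LLN above 105) | 105 to 90 (fall 15) | not counted | counted |

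The LLN matters because the appendix replaces its fixed cut-off with the local LLN where that is lower. With a platelet LLN of 95 or below, a baseline of 95 passes the baseline condition and the fall to 15 is counted.

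**4. Ceiling on the count.** The SAP says "At least 12 participants are needed to enroll in each weight group". If k of 12 children are at PCSV level at baseline on one of the 15 tests, the largest possible SAP count is 12 − k: for k = 1, 11/12 = 91.7%; for k = 3, 9/12 = 75.0%. The all-subjects count can reach 12/12.

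**5. Chance that any child is affected on a given test.** The documents give no share q of children with a PCSV-level baseline. As an assumption, take q from 5% to 30%. The chance of at least one such child is 1 − (1 − q)^n:
- n = 12: 1 − 0.95^12 = 46%, and 1 − 0.70^12 = 99%.
- n = 28 (planned total): 1 − 0.95^28 = 76%, and 1 − 0.70^28 is over 99%.

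SAP section 1 says enrollment was paused on December 28, 2021, so the achieved number may be smaller.

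**The case against.** The strongest reply is that the safety reporting has other routes:
- SAP 5.8.3 also lists all local laboratory values.
- Protocol 10.1.1 makes an isolated abnormal result an adverse event if it is symptomatic, needs corrective treatment or is one in the investigator's judgment. Worsening of a pre-existing condition counts as treatment-emergent.
- Protocol 9.2.5 requires significantly abnormal results to be repeated.
- An independent committee reviews safety data.

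The trial is also descriptive and uncontrolled, its safety endpoint is adverse events rather than PCSVs, and the schedule of events has one required post-dose laboratory draw, at day 29. All of this stands, and it limits how serious the point is. It does not restore the count: adverse-event reporting depends on symptoms, treatment or judgment, and the PCSV listing covers only participants who meet a criterion.

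Two stronger readings are tempting, and the documents support neither.
- A reader might infer that any child with an abnormal baseline is excluded. The bar is a baseline already past the PCSV threshold. A child outside the normal range but short of the threshold is counted on crossing it, as platelets 120 to 90 show. Protocol 7.2.1 also admits children with obesity, lung disease, diabetes or neurologic conditions, in whom such baselines need not be common.
- A reader might infer that deterioration in these children goes unseen, or that the reported rate is too low by a calculable amount. The other routes answer the first. For the second, the documents give no rate of PCSV-level baselines or of worsening. The protocol's all-subjects count would not measure worsening either, since it includes children who are stable or improving but still past the threshold.

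**Conclusion.** The point holds for the PCSV summary and the PCSV-specific listing. The SAP omits one of the two counts that the protocol requires and does not say so. On 15 of 20 tests a child at PCSV level at baseline cannot be counted for same-direction worsening; on the other 5 the route is partial. This rests on reading the protocol's normal at baseline as not meeting the PCSV criterion, and on the Appendix 10.1 rows as written. How many children are affected cannot be known from the documents. The matter should be fixed, but it changes no primary or secondary endpoint.

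**What to change.** In SAP 5.8.3 and Appendix 10.1, produce both protocol counts for each laboratory test:
- (a) all participants with any post-baseline value meeting the threshold, with the baseline condition removed;
- (b) participants who did not meet the PCSV criterion at baseline, or whose baseline is missing, with that subset as the denominator.

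The creatinine-change and hemoglobin-fall criteria have no baseline condition to remove. If one count is intended, SAP 1.2.3 should declare and justify the departure.

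The cost is SAP wording, an added count per test and a second denominator, with no new data. The drawback is that (a) includes abnormalities present before dosing; showing (b) beside it separates them. A count of worsening by CTCAE grade among children at PCSV level at baseline would be a useful extra, but the protocol does not ask for it.

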5.8.4. Analysis of Vital Signs

Individual participant laboratory parameter measurements will be evaluated by PCSV criteria (See [Appendix 10.1](#)), specifically identifying participants with at least one post-baseline measurement that meets the PCSV criteria.

Listings of vital sign measurements at all timepoints for the participants that meet PCSV criteria will be provided. Listings of vital signs for all participants will also be provided.

5.8.5. Analysis of 12-Lead ECG

There are no ECG data collected in this study.

5.8.6. Physical Exams

There is no specific physical exams data collected in this study. Any abnormal findings will be included in either medical history or TEAE summary depending on the timing of the abnormal findings.

5.9. Analysis of Pharmacokinetic Data

5.9.1. Analysis of Pharmacokinetic Data

Analysis will be performed according to two groups:

- Group A: body weight ≥ 10 kg to < 40 kg
- Group B: body weight ≥ 3 kg to < 10 kg

The concentrations of total casirivimab and total imdevimab over time will be summarized by descriptive statistics for each weight group.

Participants who test positive for SARS-CoV-2 infection during the treatment period may be analyzed separately from the PK analysis population.

Stratification of the analysis may be performed if participants receive a treatment that has the potential to impact the pharmacokinetics of casirivimab+imdevimab (eg, IVIG)

No formal statistical hypothesis testing will be performed.

5.10. Analysis of Immunogenicity Data

5.10.1. Analysis of ADA Data

The immunogenicity variables described in Section [4.8](#) will be summarized using descriptive statistics. Immunogenicity will be characterized per drug molecule by ADA status, ADA category and maximum titer observed in participants in the ADA analysis sets. For samples confirmed as drug specific ADA positive, but found negative at the lowest titer dilution, the lowest dilution in the titer assay is imputed.

The ADA status of each participant may be classified as one of the following:

Positive

Pre-existing - If the baseline sample is positive and all post baseline ADA titers are reported as less than 9-fold the baseline titer value

Negative - If all samples are found to be negative in the ADA assay.

The ADA category of each positive participant is classified as:

Treatment-boosted - A positive result at baseline in the ADA assay with at least one post baseline titer result \geq 9-fold the baseline titer value

Treatment-emergent - A negative result or missing result at baseline with at least one positive post baseline result in the ADA assay.

The maximum titer category of each participant is classified as:

Low (titer $<1,000$)

Moderate ($1,000 \leq$ titer $\leq 10,000$)

High (titer $>10,000$)

The following will be summarized by treatment group and ADA titer level:

- Number (n) and percent (%) of ADA-negative participants
- Number (n) and percent (%) of pre-existing participants
- Number (n) and percent (%) of treatment-emergent ADA positive participants
 - Number (n) and percent (%) of persistent treatment-emergent ADA positive participants
 - Number (n) and percent (%) of indeterminate treatment-emergent ADA positive participants
 - Number (n) and percent (%) of transient treatment-emergent ADA positive participants
- Number (n) and percent (%) of treatment-boosted ADA positive participants

Listing of all ADA titer levels will be provided for participants with pre-existing, treatment-emergent and treatment-boosted ADA response.

